### 11.3 Efficacy Analysis

The efficacy and biomarker analyses will be conducted for the FAS and the EFS.

For Phase I, descriptive summaries will be presented by cohort.

#### Overall Response Rate:

Subjects with measurable disease who receive at least 1 cycle of OP-1250 and have a post treatment tumor assessment will be included in the determination of the ORR. [REDACTED]

[REDACTED] The estimate of the ORR will be accompanied by 2-sided 95% exact confidence intervals. The ORR will be determined using RECIST 1.1 (see [Appendix E](#)) for the entire body (which include both CNS and non-CNS disease) [REDACTED]

Subjects without measurable disease will not be included in the determination of ORR; however, they will be included in safety, secondary, and exploratory analyses where appropriate.

#### Clinical Benefit Rate

Clinical Benefit Rate (CR+PR+SD  $\geq$  24 weeks) and iCBR (intracranial CR + intracranial PR + subjects with intracranial SD for  $\geq$  24 weeks in the CNS) will be estimated and will be accompanied by 2-sided 95% exact confidence intervals.

### **11.3.1 Pharmacokinetic Analyses**

Pharmacokinetic parameters will be determined for the PKAS using standard compartmental or non-compartmental methods. A listing of subjects excluded from the analysis set and individual data points excluded from the analysis will be provided. The final analysis of PK parameters will be calculated based on actual sample collection time, rather than scheduled times. For the purpose of dose escalation decisions, if actual sample collection times are not available from the database, the scheduled times may be used.

A listing of PK blood sample collection times as well as derived sampling times will be provided. OP-1250 concentrations will be summarized using appropriate descriptive statistics (eg, N, arithmetic mean, standard deviation, minimum, median, maximum, coefficient of variation [CV] %, geometric mean and CV associated to the geometric mean) for each cohort

per cycle and day. Concentrations that are below the limit of quantitation will be treated as zero for the computation of descriptive statistics and listed with the lower limit of quantitation indicated. Missing concentrations will be omitted from the calculation of descriptive statistics.

Plots of mean OP-1250 concentration-time data will be presented for each dose level per cycle. Individual OP-1250 subject concentration-time data for each cycle will be graphically presented on linear and semi-logarithmic scales.

PK parameters (non-exclusive) are described in [Table 13](#):

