**Table 13: Pharmacokinetic Parameters**

Parameter	Definition
$C_{max}$	Observed maximum plasma concentration during a sample interval.
$C_{min}$	Minimum observed concentration during a sampling interval.
$t_{max}$	Observed time to maximum plasma concentration during a sampling interval.
$t_{min}$	Time of first minimum observed concentration.
$\lambda_z$	Elimination rate constant, determined by linear regression of the terminal points of the log-linear plasma concentration-time curve. Visual assessment will be used to identify the terminal linear phase of the concentration-time profile. A minimum of 3 data points will be used for determination ( $C_{max}$ excluded).
$t_{1/2}$	Terminal elimination half-life, determined from the quotient $0.693/\lambda_z$ .
$AUC_{0-t}$	Area under the plasma concentration-time curve from time zero to the last measurable time point calculated by log-linear trapezoidal summation.
$AUC_{0-\infty}$	Area under the plasma concentration-time curve from time zero to infinity, calculated by log-linear trapezoidal summation and extrapolated to infinity by addition of the last observed quantifiable plasma concentration divided by the elimination rate constant $\lambda_z$ (if %AUC ext > 20%, $AUC_{0-\infty}$ will not be reported).
$AUC_{ext}\%$	The percent of the area under the concentration-time curve which was extrapolated to infinity (%), calculated as $(C_{last}/\lambda_z)/AUC_{0-\infty} * 100$ .
$CL/F$	Apparent clearance after oral administration, calculated from the quotient dose / $AUC_{0-\infty}$ .
$V/F$	Apparent volume of distribution after oral administration.

In addition, the PK sparse exposure data from this study may be used in the development of population PK and PK/PD models. Pharmacokinetic plasma levels and parameters will be determined, listed, and summarized for the PKAS in the PK Analysis Plan (PKAP). Only samples with acceptable PK (as defined in the PKAP) will be included in the summary statistics and a listing of individual data points or subjects excluded from the analysis will be presented. Plasma concentrations will be listed by subject for the PK Population. Summary statistics of OP-1250 concentrations will be reported by dose level, Day and Cycle. Details of this analysis will be provided in the PKAP. Possible relationships between PK parameters, PD variables, safety, and efficacy may be examined.

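### Setting concentrations below the quantitation limit to zero makes the geometric mean zero and the geometric CV undefined wherever such a value occurs (minor)

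*Protocol*

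**What the plan says.** Protocol Section 11.3.1 states that "OP-1250 concentrations will be summarized using appropriate descriptive statistics". The examples it gives are the usual arithmetic summaries followed by the "geometric mean and CV associated to the geometric mean", by cohort, cycle and day. The next sentence is the rule for values below the limit of quantitation (BLQ): "Concentrations that are below the limit of quantitation will be treated as zero for the computation of descriptive statistics". Missing values have their own rule: "Missing concentrations will be omitted from the calculation of descriptive statistics". A BLQ result is therefore not treated as missing. It stays in the summary with the value 0.

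Neither document contains another BLQ rule. The text after Table 13 says "Details of this analysis will be provided in the PKAP" and "Only samples with acceptable PK (as defined in the PKAP) will be included in the summary statistics". The Synopsis makes the same reference to the PK analysis plan (PKAP), and SAP Section 12 sends all PK analysis to a separate plan. That plan is not among the documents.

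Plasma levels of OP-1250 are listed under the primary endpoints of both phases (Protocol Table 5; SAP Section 3).

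**The concern.** The two statements cannot both be carried out. The geometric mean and its CV are computed from logarithms, and zero has none. So this is a stated rule that breaks a stated summary, rather than a detail left open.

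At stake is prespecification. When the tables are built, someone must print a zero, leave the cell blank, drop the value or substitute another. The plan does not say which, the choice would be made with data in hand, and the results differ considerably between choices.

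**Working it through.** The plan states no figure on this point, so there is nothing to reproduce. The check is of the definitions. I read the summaries as being made at each nominal sampling time within a cycle and day.

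**Formulas**
- Geometric mean: GM = (x₁ × … × xₙ)^(1/n) = exp(mean of ln xᵢ).
- Geometric CV: 100 × √(exp(variance of ln xᵢ) − 1).

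If any xᵢ = 0, the product is 0 and GM = 0 for every n and whatever the other values. On the log scale ln 0 does not exist, so the variance of the logs, and with it the geometric CV, is undefined.

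**Illustration.** Six subjects, the upper end of the 3 to 6 per cohort in Protocol Section 11.4.1. The concentrations 5, 8, 10, 12 and 20 ng/mL, one BLQ result, and a lower limit of quantitation (LLOQ) of 1 ng/mL are all assumptions.

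| Handling of the BLQ value | n | GM (ng/mL) | Geometric CV |
|---|---|---|---|
| Zero, as written | 6 | 0 | undefined |
| LLOQ/2 = 0.5 | 6 | 48,000^(1/6) = 6.03 | 211% |
| Omitted | 5 | 96,000^(1/5) = 9.92 | 54.6% |

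With the zero kept, the arithmetic mean is 55/6 = 9.17, the SD 6.77 and the median 9.0. The failure is confined to the geometric statistics.

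**How often a summary would be hit.** The chance of at least one BLQ value among n subjects is 1 − (1 − p)ⁿ. The documents give no BLQ rate, so p is varied by assumption; n = 30 is the planned size of each expansion dose group.

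| n | p = 2% | p = 5% | p = 10% | p = 20% |
|---|---|---|---|---|
| 3 | 6% | 14% | 27% | 49% |
| 6 | 11% | 26% | 47% | 74% |
| 30 | 45% | 79% | 96% | >99% |

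**Where BLQ values can be expected**
- Cycle 1 Day 1, pre-dose: Protocol Table 2 schedules a PK sample before any drug has been given. Concentrations there are BLQ in every subject, so the geometric summary fails by design.
- Early samples after the first dose (0.5 hours onward in Table 2): possible, but the documents give no basis for a rate.
- Steady state: unlikely. Dosing is daily, Protocol Section 6.2 reports a long half-life in all species tested, and Section 6.3 models an average concentration of 50 ng/mL at the 30 mg starting dose.

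**The case against.** The strongest reply has three parts.

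1. The list of statistics is introduced as examples of what is appropriate, and details are left to the PKAP, which is where a BLQ rule for geometric statistics would normally sit. It may well be there. That limits the weight of the point but does not remove it: the protocol does not stay silent, it prescribes zero without exception, and a different rule in the PKAP would contradict it.
2. The one certain case is harmless. Before the first dose zero is the true concentration, and nobody interprets a geometric mean there. This stands.
3. Any replacement rule is a convention. In the illustration LLOQ/2 gives a geometric CV of 211% and omission gives 54.6%, so neither is neutral. This also stands, and it is a reason to name the rule in advance rather than to prefer a particular one.

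A reader might infer more than the documents support:

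- *That the rule fixes Cmin on Cycle 1 Day 1 at zero.* Table 13 defines Cmin as "Minimum observed concentration during a sampling interval". The zero rule governs descriptive statistics of concentrations, not the derivation of Table 13 parameters. Whether the pre-dose sample belongs to that interval is a separate question, and if it does, it would be the lowest value under any BLQ convention.
- *That the comparison of 60 mg with 120 mg is distorted.* No section makes these geometric summaries the basis of that comparison. Protocol Section 8.8.4 reports dose-proportional exposure at the two doses and 120 mg as already selected.
- *That the geometric means will be biased upward by a calculable amount.* This needs assumed BLQ rates and software that silently drops zeros. The text says that the zeros are kept.

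**Conclusion.** The rule in Protocol Section 11.3.1 is wrong as written for the geometric mean and geometric CV. A single BLQ value in a cohort at a time point makes the first 0 and the second undefined. This follows from the definitions and needs no assumption.

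Its practical reach is small: certain but harmless at Cycle 1 Day 1 pre-dose, possible at the early samples after the first dose, unlikely at steady state. How many summaries would be affected cannot be determined, because the LLOQ and the BLQ rates are not given. The conclusion also assumes that the PKAP, not available here, does not already supply an exception. Severity: minor.

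**What to change.** In Section 11.3.1:

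- limit the zero rule to arithmetic statistics (N, mean, SD, median, minimum, maximum);
- report no geometric statistics for the Cycle 1 Day 1 pre-dose sample;
- for post-dose time points, state one rule for BLQ values in the geometric mean and geometric CV, for example LLOQ/2, omission, or not reporting the statistic;
- show the number of BLQ values at each time point.

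Carry the same rule into the PKAP so that the two agree. The cost is a sentence or two in each document, and no new data are needed. The downside is that any substitution rule is a convention, omission describes only the subjects with quantifiable concentrations, and not reporting loses the summary. Showing the BLQ count lets the reader judge.

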**Table 13: Pharmacokinetic Parameters**

Parameter	Definition
$C_{max}$	Observed maximum plasma concentration during a sample interval.
$C_{min}$	Minimum observed concentration during a sampling interval.
$t_{max}$	Observed time to maximum plasma concentration during a sampling interval.
$t_{min}$	Time of first minimum observed concentration.
$\lambda_z$	Elimination rate constant, determined by linear regression of the terminal points of the log-linear plasma concentration-time curve. Visual assessment will be used to identify the terminal linear phase of the concentration-time profile. A minimum of 3 data points will be used for determination ( $C_{max}$ excluded).
$t_{1/2}$	Terminal elimination half-life, determined from the quotient $0.693/\lambda_z$ .
$AUC_{0-t}$	Area under the plasma concentration-time curve from time zero to the last measurable time point calculated by log-linear trapezoidal summation.
$AUC_{0-\infty}$	Area under the plasma concentration-time curve from time zero to infinity, calculated by log-linear trapezoidal summation and extrapolated to infinity by addition of the last observed quantifiable plasma concentration divided by the elimination rate constant $\lambda_z$ (if %AUC ext > 20%, $AUC_{0-\infty}$ will not be reported).
$AUC_{ext}\%$	The percent of the area under the concentration-time curve which was extrapolated to infinity (%), calculated as $(C_{last}/\lambda_z)/AUC_{0-\infty} * 100$ .
$CL/F$	Apparent clearance after oral administration, calculated from the quotient dose / $AUC_{0-\infty}$ .
$V/F$	Apparent volume of distribution after oral administration.

In addition, the PK sparse exposure data from this study may be used in the development of population PK and PK/PD models. Pharmacokinetic plasma levels and parameters will be determined, listed, and summarized for the PKAS in the PK Analysis Plan (PKAP). Only samples with acceptable PK (as defined in the PKAP) will be included in the summary statistics and a listing of individual data points or subjects excluded from the analysis will be presented. Plasma concentrations will be listed by subject for the PK Population. Summary statistics of OP-1250 concentrations will be reported by dose level, Day and Cycle. Details of this analysis will be provided in the PKAP. Possible relationships between PK parameters, PD variables, safety, and efficacy may be examined.

## 11.4 Sample Size Determination

### 11.4.1 Phase I, Part A (Dose Escalation)

For Phase I, Part A (Dose Escalation), cohorts of 3 to 6 subjects will be enrolled in each OP-1250 dose group based on a rolling 6 dose escalation scheme. Each subject will participate in only 1 dose cohort. The total number of subjects to be enrolled in the dose escalation phase of the study is dependent upon the observed safety profile, which will determine the number of subjects per dose cohort, as well as the number of dose escalations required to achieve the MTD. Approximately 42 subjects will participate in Phase I, Part A (Dose Escalation) to allow for 6 planned dose levels and intermediate dose levels.

At the end of Phase I, Part A (Dose Escalation), a comprehensive review of safety, tolerability, and pharmacokinetics data will be performed to assess whether 1 OP-1250 dose can be identified as the RP2D. In the event that this comprehensive review is equivocal for 2 doses of OP-1250 as the possible RP2D, then these 2 doses will be investigated in Phase I, Part B (Dose Expansion).

### 11.4.2 Phase I, Part B (Dose Expansion)

Up to approximately 60 subjects with measurable disease will participate in Phase I, Part B (Dose Expansion). If 1 dose is clearly identified during dose escalation in Phase I, Part A (Dose Escalation) as the RP2D, then approximately 30 subjects will be enrolled at this dose. If 2 doses of OP-1250 are advanced from Phase I, Part A (Dose Escalation), then each dose will enroll approximately 30 subjects, for a total of up to approximately 60 subjects.

Subjects not evaluable may be replaced in either Part A (Dose Escalation) or Part B (Dose Expansion); therefore, approximately 102 subjects may participate in Phase I, Parts A (Dose Escalation) and B (Dose Expansion).

At the end of Phase I, Part B (Dose Expansion), a comprehensive review of safety, tolerability, PK and preliminary anti-tumor activity data will be performed. If only 1 dose was advanced from Phase I, Part A (Dose Escalation), ie, a RP2D was already identified, then the purpose of this comprehensive review will be to assess a preliminary risk:benefit ratio to enable safe enrollment of additional subjects in the Phase II. If 2 doses are advanced from Phase I, Part A (Dose Escalation), then the purpose of this comprehensive review will be 2-fold: first, to select the RP2D, and second, to assess a preliminary risk:benefit ratio of the RP2D to enable safe enrollment of additional subjects in the Phase II.

A sample size of 30 subjects per dose group will provide an estimation precision of  $\pm 19\%$  per dose group for any binary event rate assessing safety, tolerability, anti-tumor activity (eg, overall response, clinical benefit) or exposure/kinetics. This level of precision is regarded as clinically sufficient in the comprehensive review of safety, tolerability, PK, and preliminary anti-tumor activity data to gate enrollment into the Phase II part of the study.

### 11.4.3 Phase II

The Phase II part of the study is designed to assess safety and to obtain a preliminary estimation of anti-tumor activity of OP-1250 in metastatic breast cancer subjects. A total of approximately 50 subjects with measurable disease who do not have CNS metastasis will be

treated at the RP2D. Subjects enrolled in the dose expansion (Phase I, Part B) at the RP2D will contribute to the estimation of anti-tumor activity. In addition, 2 exploratory cohorts will be enrolled consisting of approximately 15 subjects each: 1) subjects with non-measurable disease, and 2) subjects with CNS disease. Subjects not evaluable may be replaced; therefore, approximately 88 subjects will participate in the Phase II part of the study.

At the end of Phase II, a comprehensive review of the safety and preliminary anti-tumor activity data of all 50 subjects with measurable disease dosed at the RP2D will be performed to obtain a preliminary risk:benefit profile to guide further drug development of OP-1250. A sample size of 50 subjects will provide an estimation precision of  $\pm 15\%$  for any binary event assessing safety (eg, any SAEs) or anti-tumor activity (eg, overall response, clinical benefit). This level of precision is regarded as clinically sufficient in the preliminary assessment of the risk:benefit profile to plan future clinical trials for OP-1250.

Subjects without measurable disease are being enrolled in the Phase II study in order to mimic the general population of ER+ breast cancer subjects, many of which have bone only disease. Subjects without measurable disease in the Phase II are limited to a total of 15 subjects and will not be included in the determination of ORR; however, they will be included in safety, secondary, and exploratory analyses where appropriate.

Anti-tumor activity data of all 50 subjects dosed at RP2D will be examined. The respective mutation status cohort may be expanded further if the comprehensive review of its safety and preliminary anti-tumor activity data indicates favorable risk:benefit ratio for these subjects with metastatic or locally advanced breast cancer for which standard curative measures do not exist.

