### 8.12 Blinding

This is an open-label study with no placebo or comparators.

	OP-1250-001	Page 71 of 111
---	-------------	----------------

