6. GENERAL ANALYSIS CONSIDERATIONS

6.1 Statistical Analysis Cohorts

Statistical analysis will be conducted in the cohorts below.

1. Dose Escalation subjects: All endpoints [REDACTED] will be summarized by dose groups.
2. Subjects treated at 60 mg or 120 mg pooled from dose escalation, dose expansion and phase II (without cohort C): The study subjects and demographic, pharmacodynamic endpoints, and efficacy endpoints will be analyzed by dose groups.

- [REDACTED]
4. All subjects: All safety related endpoints will be summarized based on the safety analysis set by dose groups, [REDACTED] and overall.

For summary by dose groups, the dose groups will be based on the first doses the subjects received.

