10. EFFICACY ANALYSES

Efficacy analyses for ORR [REDACTED] by investigator assessment will be conducted using EFS with measurable disease at baseline (without cohort C). CBR by investigator assessment will be summarized using CBR analysis set. [REDACTED]

[REDACTED]

[REDACTED]

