10.2 Methods Of Efficacy Analysis

The ORR and CBR will be summarized with frequencies and percentages. The exact 95% confidence interval (CI) via the Clopper-Pearson method will be constructed for the ORR and CBR.

A waterfall plot will plot the best percentage change from baseline (or maximum decrease from baseline) in sum of the longest diameters (short axis for measurable lymph node) of target lesions for each subject, plotted in order from greatest percentage change to smallest. The OP-1250 dose will be presented in the plot with different colors. Changes in tumor burden by time point may be summarized.

A swimmer's plot will display overall tumor response over time and include prior therapies in the advanced setting. Patients will be grouped by OP-1250 dose.

[REDACTED]

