10.6 Interim Analysis and Data Monitoring

No formal interim analysis will be conducted.

[REDACTED]

[REDACTED]

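### The SAP is inconsistent on whether subjects added under the protocol's response-driven mutation-status expansion enter the Phase II primary ORR, and one of its two rules can give an enriched estimate with an under-covering interval

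*Protocol*

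**What the plan says.** Protocol 11.4.3 plans about 50 measurable-disease subjects without CNS metastases at the RP2D. It states that "A sample size of 50 subjects will provide an estimation precision of" ±15%, and then that "Anti-tumor activity data of all 50 subjects dosed at RP2D will be examined". The next sentence is the permission at issue: "The respective mutation status cohort may be expanded further if the comprehensive review of its safety and preliminary anti-tumor activity data indicates favorable" risk and benefit. No response threshold, number of added subjects or analysis rule follows. Protocol 8.12 confirms that responses are visible throughout: "This is an open-label study with no placebo or comparators".

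The SAP describes the ORR population in two ways.

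- SAP 5.3 says the ORR analyses use data from the 50 Cohort A subjects treated at the RP2D.
- SAP 6.1, item 2, defines the efficacy cohort as "Subjects treated at 60 mg or 120 mg pooled from dose escalation, dose expansion and phase II (without cohort C"), analysed by dose group. SAP 10 says the ORR analysis "will be conducted using EFS with measurable disease at baseline (without cohort C"), and SAP 10.1 defines confirmed ORR on the same set. None of these has a cap or a cut-off at the 50th subject.

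For the interval, SAP 10.2 says: "The exact 95% confidence interval (CI) via the Clopper-Pearson method will be constructed for the ORR and CBR". SAP 10.4 plans no covariate adjustment, so nothing would weight the result back to the starting mutation mix. SAP 10.6 says: "No formal interim analysis will be conducted". No readable SAP passage mentions the mutation-status expansion.

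**The concern.** The Phase II primary objective is the ORR in HR-positive/HER2-negative subjects without CNS metastases. It is not the ORR in a population whose mutation mix depends on which group responded better. A programmer following SAP 6.1, 10 and 10.1 would put expansion subjects at 120 mg into the same numerator, denominator and Clopper-Pearson interval as the subjects whose responses prompted the expansion. A programmer following SAP 5.3 would leave them out. The headline activity result therefore depends on which section is followed, and one choice makes sample size and population mix depend on the outcome.

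At stake is the meaning of the reported ORR and the coverage of its interval. No hypothesis test is involved in the readable text, so this is not a type I error question.

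**Working it through.** **The plan's own figure.** For 25 responders among 50, the two-sided 95% Clopper-Pearson interval is 35.5% to 64.5%, a half-width of 14.5 points. The stated ±15% is reproduced. For 30 subjects the half-width is 18.7 points, matching the ±19% in Protocol 11.4.2.

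**Inputs from the documents.**
- 50 subjects (Protocol 11.4.3).
- Mutation prevalence of 20% to 40% (Protocol 6.1, background on previously treated patients), giving k = 10, 15 or 20 mutant subjects among the 50.
- Phase II ceiling of 88 against 50 + 15 + 15 = 80 planned, leaving 88 − 80 = 8 places (SAP 4).

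**Assumptions, not in the documents.** True ORR pM (mutant) and pW (wild-type); the mutant cohort is expanded if its observed ORR is at least 20%; m = 8, 15 or 30 subjects are added.

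**Formulas.** The target is the ORR of the unexpanded mix, θ = [k·pM + (50 − k)·pW]/50. With x mutant and w wild-type responders among the 50, and a responders among those added, the estimate is (x + w + a)/(50 + m) if expanded and (x + w)/50 if not. Summing exact binomial probabilities over x, w and a gives the mean bias and the probability that the Clopper-Pearson interval excludes θ.

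**One case by hand** (k = 10, m = 30, 25% vs 10%):
- θ = (10 × 0.25 + 40 × 0.10)/50 = 13%.
- P(expand) = P(x ≥ 2) = 1 − 0.75^10 − 10 × 0.25 × 0.75^9 = 0.756.
- The mutant share rises from 10/50 = 20% to 40/80 = 50%. The change of mix alone shifts the ORR by 0.30 × 15 = 4.5 points.
- Full enumeration: +5.2 points given expansion, +3.1 on average; the interval misses 14.3% of the time.

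**Results for 25% vs 10%** (values for k = 10 / 15 / 20):

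| Subjects in the ORR | Mean bias, points | Two-sided miss, % |
|---|---|---|
| Planned 50 only | 0 | 3.0 / 3.7 / 2.8 |
| 50 + 8 | +1.1 / +1.0 / +0.8 | 4.2 / 4.9 / 3.8 |
| 50 + 15 | +1.9 / +1.6 / +1.4 | 7.9 / 8.4 / 7.1 |
| 50 + 30 | +3.1 / +2.6 / +2.2 | 14.3 / 14.6 / 8.5 |

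**Other rates.**
- 20% vs 10%: with 8 added, bias +0.3 to +0.6 points and miss 3.2% to 4.5%; with 15 or 30 added, miss 5.0% to 8.4%.
- Equal rates, over 800 settings (ORR 10% to 30%, trigger 15% to 30%, 8 to 50 added): bias −1.25 to 0 points, miss 1.5% to 5.0%.
- A 20-point difference (wild-type ORR 10% to 20%, trigger 20% or 25%): miss 3.8% to 6.1% with 8 added and 7.8% to 14.7% with 20 added.

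**The case against.** The strongest reply is that SAP 5.3 already confines the ORR to the 50 Cohort A subjects. It is the only SAP sentence that ties the ORR to a number of subjects. A reader might infer from SAP 6.1 and 10 that pooling is simply the SAP's rule. The documents do not support that: pooling is one side of a conflict. But SAP 5.3 is a sample-size section and the uncapped sets stand in the analysis sections, so it does not settle the matter.

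A reader might also infer that enrichment and under-coverage follow from the expansion clause itself. They do not. Both need a true ORR difference by mutation status, and no document gives ORR by mutation status. Material under-coverage also needs more subjects than the 8 places between 80 and 88, which are meant for replacements. Protocol 11.4.3 does not tie the expansion to that ceiling, so a larger one is not excluded, but 15 or 30 is an assumption.

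A third inference is that the expansion contradicts SAP 10.6. Protocol 11.4.3 places the comprehensive review at the end of Phase II, on the 50 subjects, and the expansion clause most naturally refers to that review. An end-of-phase review is not an interim analysis. On this reading the development decision can also be taken on the 50 before any expansion subject exists. What remains exposed is the ORR reported afterwards.

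Finally, SAP text is redacted at the end of 5.3, at item 3 of 6.1, within 10 and between 10.6 and 10.8, and may cover mutation-status analyses. For that reason no criticism is made of a mutation-subgroup ORR, which no readable passage defines. The conflict among the readable rules stands.

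**Conclusion.** The point holds as an unresolved conflict over the primary ORR population, one side of which lets observed responses determine the mutation mix. If the SAP 6.1/10 rule is followed, ORR is 25% in mutant and 10% in wild-type subjects, the trigger is an observed 20%, and 15 or 30 subjects are added, the mean bias is about +1.4 to +3.1 points and the nominal 95% interval misses 7% to 15% of the time. With only 8 added, the miss is about 3% to 5% at the 25%/10% and 20%/10% rates, and up to 6.1% for a 20-point difference. With equal rates there is no inflation. If SAP 5.3 is followed, there is no bias and coverage stays within nominal.

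This should be corrected, since it concerns the primary efficacy endpoint and the remedy is cheap. It does not show that the trial's ORR will be wrong. Confidence is medium, because expansion size, trigger and response rates are assumed and some SAP text is redacted.

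**What to change.** In SAP 6.1, 10 and 10.1:

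1. State that the primary Phase II ORR and its exact interval use the planned 50 RP2D Cohort A subjects, as in SAP 5.3, and exclude anyone enrolled under the mutation-status expansion.
2. Report expansion subjects separately, with their own ORR and Clopper-Pearson interval.
3. Label any ORR that combines expansion subjects with the planned 50, or with those of the same mutation status among them, as exploratory.

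SAP 10.6 needs no change.

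The cost is SAP wording and one extra table, with no additional patients or procedures. The downside is precision: an estimate from new subjects only has an exact 95% half-width of up to about 26 points for 15 subjects or 19 points for 30. The headline ORR may also be slightly lower than a pooled one.
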